Infections resulting from health-care complications are the greatest cause of morbidity and mortality in hospitalized patients in the US. [1] Urinary tract infection (UTI) is the most common health care complication following surgery. [2] Rates are high, causing longer hospital stays, readmissions, and antibiotic use. Rates at UCH are near 40%, high compared to the national standard. About 15% of post-op complications result in extended stays or readmissions and costly antibiotic treatments. These infections should be preventable with prophylaxis and pre-treatment protocols but there is no standard protocol at UCH for minimizing the risk of UTI infection. We propose a catheter management protocol in which the catheters are treated with betadine and then inserted while remaining protected within the plastic sleeve, reducing airborne/contact exposures to the catheter. Betadine is a topical antiseptic used in the prevention of infections. It is widely available and a cost-effective intervention. Similar aseptic protocols have been tested and implemented in other countries however we lag behind in having a systematic protocol for reducing the incidence of UTIs complications.[2-4] A study in rural-India found that antiseptic techniques were the best preventable measure for device-related infections.[5] Patients currently receive what will be considered standard of care intra-operative catheter placement which involves placement of catheter in a sterile field, drainage to a closed system and shortest possible duration of catheter placement. We hypothesize that the implementation of a controlled antiseptic protocol to inserting the urinary catheter will reduce UTI rates following surgery.

III. Preliminary Studies/Progress Report:

The Gynecologic Oncology service performs between 15-20 surgeries per week. There are 5 providers who would require training in the protocol. The providers all have similar practice patterns as they pertain to current standard of care catheter placement. Training would be relatively straight forward and protocol adherence is expected to be high. Adherence can be monitored on the service by the principle investigator. Faculty Mentors include [name] who is an assistant professor in the department of Obstetrics and Gynecology at the UCH. He serves as the Principal Investigator for the Gynecologic Oncology Group, a national research consortium. His research has focused on all gynecologic cancer sites and surgical improvements.

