be assessed for symptoms of UTI since surgery by assessment of: urethral discomfort, suprapubic tenderness or pelvic pain, sense of urinary urgency, frequency or dysuria, fever, antibiotic use, and clinical and laboratory data suggesting infection (UA with +leukocyte esterase +/- nitrates, urine culture with $>10^5$ bacterial colony forming units per mL (CFU)). Asymptomatic bacteriuria will be considered a UTI for this study (defined as $>10^5$ CFU/mL on urine culture). Patients who are treated with antibiotics for UTI without laboratory data suggesting infection will be included in UTI group. For participants reporting ED visits prior to 14 +/- 2 day visit, ED reports will be obtained and an assessment will be made regarding the symptomatic UTI diagnosis. Those meeting these criteria will be followed with symptom and laboratory analysis. All positive UA test will be confirmed by laboratory analysis for final diagnosis. Results of +leukocyte esterase +/- nitrites will be considered abnormal. If a diagnosis of UTI does not exist in the patient chart outside of study, the patient's clinical picture will be evaluated independently by 2 separate care providers to determine if meeting criteria for UTI (symptomatic bacteriuria as defined above). If there is discrepancy a third provider will be the determining opinion. Participants meeting the primary endpoint (UTI) will be discontinued from the study following.

Secondary outcomes include: hospital length of stay, readmissions, antibiotic use at the time of surgery and post-surgery. Measures of UTI, and secondary outcomes will be collected from observation during study visits and from the patient medical charts., If closed drainage system was disrupted during placement (to back fill bladder intra-operatively), and method of catheter discontinuation ("fill and pull" versus "pull and void" methods) will be collected for comparison between the groups for analysis as a possible confounding variables.

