Additional secondary outcomes to be evaluated will include patient discomfort with catheter, tolerability of catheter, length of hospital stay, and number of post-operative evaluations required. A cost-analysis will be performed as a secondary endpoint based on this cost factors (length of hospital stay, readmission, additional clinic/ED visits, antibiotic costs). Costs of hospital days, clinic visits, other appointments, and antibiotics will be standardized for evaluation based on literature for cost analysis in gynecologic oncology literature.

b. Target population. Women undergoing extended surgery lasting >1 hour and requiring urinary catheter will be eligible for enrollment. All patients will have surgery performed by one of the trained Gynecologic Oncologists at the University of Colorado Hospital.

Inclusion criteria will include:

- 1) women 18-89 years of age
- 2) admitted for surgery lasting >1 hour and requiring urinary catheter,
- 3) have normal urine analysis within 24 hours pre-surgery, and
- 4) able to provide informed consent.

Women with dialysis, chronic urinary infection, and current infection will not be eligible to participate. Women who are pregnant or breast feeding will not be included in the study. Men will not be included because of their lower incidence of UTIs compared to our female population.

The null hypothesis is that there will be no difference in UTI rates between the standard of care catheter placement and the sterile protocol placement. If we use the current rates of UTI after catheter placement described above at 40%, we would need to enroll 100 patients per arm (total 200) to see a 50% reduction in UTI rates in the intervention group with an alpha of 0.05 and a power of 0.84. The Gynecologic Oncology services averages around 5 surgical patients who would be eligible for this study per week. We anticipate needing between 10-12 months to complete enrollment.

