- Consent and randomization: Patients will be randomized to standard of care intraoperative catheter placement versus aseptic protocol for catheter insertion upon providing informed consent. Randomization will be performed using the REDCap randomization module and will be performed by the study coordinator or research manager.
- Urine analysis with urine dip: Patients will be asked to provide a clean catch urine sample in provided collection cup prior to surgery (done as standard of care), a catheter collected urine sample at 24hrs post-operatively (research procedure) and another clean catch specimen at their 2-week surgical follow-up (research procedure). This collection and analysis is low risk except for the possibility of unnecessary treatment if abnormal sample is obtained. Abnormal samples will be correlated with patient history/complaints and confirmed with formal urine analysis. Confirmation of UTI would also utilize urine culture. The urine analysis by dip gives a fast yet reliable indicator of urinary tract infections. Pre-operative/pre-randomization allows us to exclude patients who may have underlying UTI prior to initiation of the study.
- Catheter placement: The aseptic protocol involves dipping standard catheter in an aseptic betadine solution and leaving a pre-existing plastic cover in place over the catheter during insertion and while in place. We do not anticipate any added risk of the aseptic protocol to the patient although patients may experience some increased irritation due to the protective plastic cover.

Anticipated Risks

While the study anticipates minimal risks, the following outlines any potential minimum risk to subjects:

- i. **Breach of Confidentiality:** Data obtained using information from medical records poses minimal risk. All procedures in which information is being obtained will be conducted per standard of care. There is a risk that a patient's privacy may not be protected. This risk is uncommon.

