- Information that indicates a change to the risks or potential benefits of the research

Adverse events that are deemed not related will be documented in the study AE log, subject study charts, and reported to COMIRB at the time of annual review, per their policy. The PI will review AEs on an ongoing basis.

Anticipated clinical adverse events associated with urine catheter is: urethral/bladder irritation requiring removal of catheter prematurely, bladder or urethral injuries related to catheter placement, folliculitis of the genital area, change in urine color and UTI infection. Symptoms of a UTI are anticipated and include: fever, chills, urethral discomfort, incontinence, dark urine, urinary pain, suprapubic tenderness or pelvic pain, urinary urgency, frequency or dysuria, antibiotic use, prolonged hospital stay or readmission following symptoms. Severe UTIs may result in spread to the kidneys and present with abnormal kidney function assessment.

Anticipated clinical adverse events associated with the use of Betadine are as follows:

- **Common:** skin irritation (burning, redness, or general irritation)
- **Rare but Severe:** severe allergic reaction including rash, gives, itching, difficult breathing, tightness of the chest, swelling of the face, lips or tongue.
- **Unlikely:** balance/hearing problems, hair bumps (folliculitis), change in the amount of urine

There are no known contraindicated medications associated with the use of Betadine.

Serious Adverse Event

A Serious Adverse Event (SAE) is any untoward medical occurrence at any dose that:

- Results in death
- Is life-threatening (defined as an event in which the subject was at risk of death at the time of the event; it does not refer to an event which hypothetically might have caused death if it were more severe)

- Requires inpatient hospitalization or causes prolongation of existing hospitalization (see *NOTE**: below for exceptions)
 - Results in persistent or significant disability/incapacity
 - Is a congenital anomaly/birth defect
- Is an important medical event, defined as a medical event that may not be immediately life-threatening or result in death or hospitalization but, based on appropriate medical and scientific judgment, may jeopardize the subject or may require intervention (e.g., medical, surgical) to prevent one of the other serious outcomes listed above.
- Suspected transmission of an infectious agent (e.g., pathogenic or non-pathogenic) via the study treatment is an SAE.

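### Closed-system disruption and catheter-removal method arise after randomisation and should not be treated as confounders; catheter duration is missing from the listed data

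*Combined protocol and SAP*

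**What the plan says.** Section IV.a lists two items of catheter care: disruption of the closed system to back-fill the bladder during surgery, and removal by fill-and-pull or by pull-and-void. It says that they "will be collected for comparison between the groups for analysis as a possible confounding variables".

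Section IV.c randomises 1:1 before surgery, and Visit 2 in section IV.d places this on the day of the procedure. The operating physician inserts the catheter, the sleeve stays on after the operation, and no masking is described. The same section asks for the same infection-control practices in every participant.

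Section VI makes the primary comparison a test of two binomial proportions at 24 hours and at 14 +/- 2 days, under intention to treat. It then compares the arms on symptomatic and demographic covariates and carries those that differ significantly into logistic models for UTI. The discussion of scientific problems in section V also relies on randomisation together with adjustment in the analysis to limit confounding.

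On catheter time, section II describes standard care as including "drainage to a closed system and shortest possible duration of catheter placement". Section IV.e warns that "patients may experience some increased irritation due to the protective plastic cover", and the adverse-event section anticipates "urethral/bladder irritation requiring removal of catheter prematurely". The data lists in sections IV.a to IV.d include no insertion time, removal time or duration.

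**The concern.** A confounder of a randomised comparison would have to be a cause of allocation or share a cause with it. Neither is possible for events that follow allocation. If back-filling or removal method differs by arm beyond chance, the difference is a consequence of the protocol or of staff knowing the arm. A model that conditions on it no longer estimates the total effect of the protocol. It can also introduce bias where an unmeasured factor, such as difficulty of surgery, drives both catheter handling and UTI.

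The entry rule in section VI makes this more likely. Choosing covariates because they differ between arms favours exactly those variables that allocation has changed. The rule is not confined to baseline data, since the symptom variables it covers also arise after randomisation.

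The second part is a gap in explanation. The documents themselves foresee irritation from the sleeve and premature removal for irritation. If catheters in the two arms stayed in for different lengths of time, the listed data would not show it, and a UTI difference could not be described alongside catheter exposure.

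**Working it through.** **1. The plan's own figure.** Inputs from section IV.b: 40% UTI under standard care; the aim "to see a 50% reduction in UTI rates in the intervention group", hence 20%; and 100 per arm "with an alpha of 0.05 and a power of 0.84".

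- Two-sided, without continuity correction: n = [1.96 √(2 × 0.30 × 0.70) + 0.9945 √(0.24 + 0.16)]² / 0.20² = (1.270 + 0.629)² / 0.04 = 90.2, so 91.
- With continuity correction: (90.2/4) × [1 + √(1 + 4/(90.2 × 0.20))]² = 99.9, so 100 per arm.

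The stated size reproduces exactly, so this point does not concern a wrong figure. The calculation is for the unadjusted comparison.

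**2. Order of events.** Randomisation comes first, then insertion by a physician who knows the arm, then any back-filling, then removal. Both care variables come after allocation.

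**3. What adjustment would do (illustration; no input here is in the documents except 40% and 20%).** Let a care factor M occur in a share q0 of the standard arm and q1 of the aseptic arm, and multiply UTI risk by r in each arm. Risk in an arm is b(1 − q + qr), so the M-adjusted risk ratio is

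RR_adj = (0.20/0.40) × (1 − q0 + q0·r) / (1 − q1 + q1·r).

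With q0 = 0.50 assumed:

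| q1 | r = 1.5 | r = 2 | r = 3 |
|---|---|---|---|
| 0.50 | 0.50 | 0.50 | 0.50 |
| 0.40 | 0.52 | 0.54 | 0.56 |
| 0.30 | 0.54 | 0.58 | 0.63 |
| 0.20 | 0.57 | 0.63 | 0.71 |

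Example: q1 = 0.30, r = 2 gives 0.50 × 1.5/1.3 = 0.58. The unadjusted comparison is 40% against 20% in every cell. If M were commoner in the aseptic arm, the shift would go the other way. The table assumes no shared cause of M and UTI; such a cause would add bias of unknown direction. I used risk ratios because odds ratios change on adjustment even when M is balanced.

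**4. How often the entry rule would pick M.** With 100 per arm and q̄ the mean of q0 and q1, the probability of a significant difference is about

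Φ{[|q0 − q1| − z √(2q̄(1 − q̄)/100)] / √[(q0(1 − q0) + q1(1 − q1))/100]}.

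For 50% against 30% at p < 0.05: (0.20 − 1.96 × 0.0693)/0.0678 = 0.95, probability 0.83. At p < 0.005, the only threshold that section VI states: 0.53. For 50% against 20%: above 0.99 and 0.96. For 50% against 40%: 0.29 and 0.08. The larger the change caused by allocation, the surer the entry into the model.

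**5. Catheter duration.** Setting section II (short duration is part of standard care), section IV.e (irritation from the cover) and the adverse-event list (premature removal) beside the data lists in section IV shows a variable that the plan treats as relevant but does not list for collection. No size can be computed, because the documents give neither catheter times nor a relation between time and UTI.

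**The case against.** The strongest reply is that the main result is untouched. A reader might infer that the primary UTI difference could be adjusted away. The documents do not support that: the primary test is unadjusted, and no catheter-care variable enters it. Section VI does not name the two variables at all, and it describes its logistic models as finding predictors of UTI for each arm. Read literally, those may be within-arm models with no arm effect to distort. This stands, and it confines the point to supportive analyses. It does not remove it, because section IV.a still gives the variables the role of confounders and section V still promises adjustment.

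A reader might also infer that a lower UTI rate would be credited to the wrong cause. Earlier removal brought about by the sleeve would be part of the total effect of the protocol, so the randomised difference stays valid; only the explanation is limited.

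Nor do the documents show that the sleeve changes care. They offer a path only through irritation and early removal; the irritation is stated as a possibility, and early removal is listed for urinary catheters generally. Nothing ties the arm to back-filling or to the choice of removal method, and equal infection-control practice is required in both arms.

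Lastly, the duration gap is partial. The case report form is not among the documents, so only absence from the listed data can be stated. Premature removal may be recorded as an adverse event, and discomfort and tolerability are secondary outcomes. These would flag some cases but would not give duration by arm. It is tempting to assume that risk is proportional to catheter time and so put a number on the possible share of the effect. Nothing in the documents supports that relation or any shortening of duration, so no such number should be used.

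**Conclusion.** The point holds in a limited form. Two post-randomisation variables have been given the wrong analytic role. The label invites an adjusted estimate that would no longer be the total effect and could be biased, and the entry rule in section VI would encourage it. The unadjusted primary comparison is unaffected.

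The range of 0.52 to 0.71 against a true 0.50 is an illustration. It rests on assumed values for how common the care factor is, how far it differs by arm and how strongly it relates to UTI. With no difference by arm there is no shift in the risk ratio. The absence of catheter duration from the listed data restricts what the trial can explain about a UTI difference, by an amount the documents do not allow one to estimate. The change is worth making because it is cheap and because catheter times may be hard to recover later.

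**What to change.** - **Section IV.a:** describe closed-system disruption and removal method as *post-randomisation catheter care, reported by arm*, and drop the reference to confounding.
- **Section VI:** state that the primary estimate is the unadjusted total effect of the protocol. Keep the two variables out of any model that estimates the arm effect. Limit adjustment in such models to baseline covariates named in advance, in place of entry by significance between arms.
- **Data collection:** add date and time of catheter insertion and removal, and the reason for removal, taken from the chart. Report duration by arm descriptively beside the primary result.

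The cost is a few extra chart fields per participant and short wording changes. No study procedure or clinical care changes, and the sample size is unaffected.

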c. Study Design and Research Method. We will conduct a single-site Randomized Control Trial (RCT) in order to examine the use of an aseptic protocol for catheter insertion during gynecologic oncology surgeries for quality improvement. This study will take place at the UCH inpatient surgical unit of gynecologic oncology. The catheter protocol for QI will be conducted in the operating room prior to surgery and will not increase prep time or operating room time. Follow-up will be conducted during standard outpatient care visits and will also not increase clinic use time.

The intervention in this study is a controlled aseptic pre-treatment protocol for catheter use in the operating room involving dipping the tip of the catheter into betadine prior to insertion and maintaining catheter in the sterile plastic sleeve during preparation, insertion and post-operatively to avoid excess exposure to the environment. The Physician performing the operation will be responsible for inserting the catheter. Patients with normal UA pre-surgery will be randomized 1:1 to one of two arms prior to surgery:

- 1) Aseptic protocol for catheter insertion using betadine treated catheter and maintaining plastic sleeve on catheter *or*
- 2) SOC catheter insertion in which catheter is inserted right out of package/non-treated catheter.

Prior to study initiation, the PI will train providers on the proper use of the protocol. Catheter insertion procedures will be documented in the operation note following surgery. Compliance will be measured by adherence to both betadine use and maintenance of plastic sleeve. Standard of care practices for infection control are to be conducted by providers on all participants. This includes: hand hygiene, inserting catheters for appropriate indications, remove catheters when no longer needed, maintain a close system keeping bag and tubing below the bladder.

We will collect general patient demographics to assure similarities between the randomized groups. These will include age, race/ethnicity, BMI, insurance type, diagnosis (reason for surgery), history of diabetes, menopausal status, and smoking status. MRN data will be collected in order to pull data directly into the OnCore data management system.

d. Study Procedures

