Participants will conduct the following study visits over 2 weeks. All costs associated with routine standard of care procedures for catheter insertions and diagnosing and treatment of a UTI will be the responsibility of the patient and/or their insurance provider. All costs associated with procedures conducted for research only will be paid for by the research study.

- **Visit 1 Screening and Enrollment:** Potential participants will be screened and consented for study up to 30 days prior to their surgical procedure. Inclusion/Exclusion criteria will be reviewed at the time of consent and baseline data including physical exam, health history, clinical diagnosis and concomitant medications will be collected following consent. A urine sample will be collected and analyzed 0-24 hours prior to procedure.
- **Visit 2 Randomization and Catheter Insertion:** Participants will be randomized to either the SOC catheter protocol or catheter insertion including Betadine on the day of procedure. Standard protocol will be followed for catheter preparation and insertion. Any adverse events following insertion will be recorded. Pre-operative antibiotics will also be recorded.
- **Visit 3, 24-hour post-op:** Patients will be assessed at 24 hours post-op in-patient. A urine sample will be collected and analyzed. Any positive urine analysis will be further analyzed and confirmed by the UCH laboratory per SOC procedures. Patients will be assessed for symptomatic signs of UTI and review of AEs following procedure.

- **Visit 4; 2-week post op:** Patients will be assessed 2-weeks post-op at their SOC post-op clinic visit. A urine sample will be collected and analyzed. Any positive urine analysis will be further analyzed and confirmed by the UCH laboratory per SOC procedures. A physical exam will also be collected. Patients will be assessed for symptomatic signs of UTI and review of AEs and ED visits since the last visit. Data including hospital stay, readmission, and antibiotic use will be collected. Patient satisfaction with catheter procedure will also be collected. Patient will be finished with study following visit 4.

e. Description, risks, and justification of procedures and data collection tools:

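### The eligibility criteria do not exclude women with a known allergy to Betadine, although the protocol lists a severe allergic reaction and allocates Betadine to half the participants

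*Combined protocol and SAP*

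**What the plan says.** Section IV.b (Target population) sets four inclusion criteria: female and aged 18 to 89, an operation of more than an hour that needs a catheter, a normal urine analysis in the 24 hours before surgery, and capacity to consent. The exclusions follow: "Women with dialysis, chronic urinary infection, and current infection will not be eligible to participate" and "Women who are pregnant or breast feeding will not be included in the study". Men are also left out.

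Section IV.c gives the allocation: "Patients with normal UA pre-surgery will be randomized 1:1 to one of two arms prior to surgery". The experimental arm is "Aseptic protocol for catheter insertion using betadine treated catheter", with the plastic sleeve kept on; the comparator catheter is untreated.

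The adverse-event part of section IV.e lists, as rare but severe, a "severe allergic reaction including rash, gives, itching, difficult breathing, tightness of the chest, swelling of the face, lips or tongue" among the anticipated events with Betadine. The only statement there about contraindications concerns medications.

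Other text describes the Betadine risk as low. The Discomforts paragraph under Anticipated Risks does not expect Betadine on the catheter to raise the risks it describes. The Serious Adverse Event text says that no serious events are known to have been reported with Betadine.

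**The concern.** The protocol names a severe reaction to the study agent, but its eligibility list does not ask whether a woman has already had one. If such a woman is enrolled and allocated to the aseptic arm, there are two outcomes. Either she is exposed, avoidably, to an agent to which she is known to react, or Betadine is withheld from her after randomisation. The second outcome has no counterpart in the control arm, where there is no Betadine on the catheter to withhold. An exclusion applied before randomisation prevents both. What is at stake is participant safety and tidy conduct.

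**Working it through.** **The plan's own figure.** The point does not depend on the sample size, but it was checked to see whether the fix would disturb it. Section IV.b gives 40% against 20%, alpha 0.05, power 0.84 and 100 per arm. It does not say whether the test is one- or two-sided; two-sided is assumed here.

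- Uncorrected: n = [1.960 × √(2 × 0.3 × 0.7) + 0.9945 × √(0.4 × 0.6 + 0.2 × 0.8)]² / 0.2² = (1.270 + 0.629)² / 0.04 ≈ 90.2, so 91 per arm.
- With continuity correction: (90.2 / 4) × [1 + √(1 + 4 / (90.2 × 0.2))]² ≈ 99.9, so 100 per arm.

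The stated 100 per arm is reproduced. An allergy exclusion changes none of these inputs.

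**Is there a criterion anywhere?** The whole document was read for any eligibility rule on allergy, hypersensitivity, iodine or Betadine. None of the inclusions or exclusions in section IV.b is one, and no other section adds one. The list shows no sign of redaction. The Data Collection and Confidentiality text treats all clinic patients who satisfy the criteria as eligible.

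**What stands between the list and exposure?**

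1. *Screening by the PI/Co-I and research team* (Data Collection and Confidentiality). They apply the listed criteria, which contain no allergy term.
2. *Informed consent* (same text). Women are told of the risks, participation is voluntary, and there is time for questions. A woman who knows that she reacts can disclose it or decline. This depends on her, not on a rule.
3. *Health history at Visit 1* (IV.d): "baseline data including physical exam, health history, clinical diagnosis and concomitant medications will be collected following consent". The criteria are reviewed at consent and the history is taken afterwards. No step sends the history back to eligibility.
4. *Randomisation at Visit 2* (IV.d): "Participants will be randomized to either the SOC catheter protocol or catheter insertion including Betadine on the day of procedure". The clinical condition stated for it in IV.c is a normal urine analysis. (IV.e instead places randomisation at the giving of consent. On that reading the history could even come after allocation, although the urine-analysis condition favours the Visit 2 reading.)
5. *Insertion* (IV.c): "The Physician performing the operation will be responsible for inserting the catheter". The physician may withhold Betadine, but by then allocation has been made. Compliance is measured partly by Betadine use (IV.c), and section VI asks only that the reason for withholding be documented.

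Steps 1 to 3 can act before randomisation, but none requires anyone to act on a known reaction.

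**Size.**

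- Chance of allocation to Betadine for an enrolled woman under 1:1: 1 / (1 + 1) = 0.5. This is not a chance of exposure or of a reaction, because the steps above may intervene.
- Accrual cost of one exclusion at about 5 eligible women per week (IV.b), if all enrol: 1 / 5 = 0.20 week.
- The same cost from the planned 200 women in 10 to 12 months: 10 months is 10 × 52 / 12 = 43.3 weeks, so 43.3 / 200 = 0.22 week; 12 months is 52 weeks, so 52 / 200 = 0.26 week.
- Number of women affected: the documents give no prevalence, so no estimate is made.

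**The case against.** The strongest reply is that several people stand between the eligibility list and any harm: the screening team, the woman herself at consent, whoever takes the history, and the physician who inserts the catheter. The exposure is a dipped catheter tip, and the protocol describes the added risk as low in two places. All of this stands, and it keeps the point small. It does not close the gap. None of these checks is a criterion, and the low-risk statements are general: they do not address women already known to react. The protocol also lists the severe reaction itself.

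A reader might infer more than the documents support:

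- *That nothing can act before randomisation.* Informed, voluntary consent is a stated route before allocation, and screening and the history may also work.
- *That the consent form asks nothing about allergy.* Consent pages were removed from the supplied text, so this cannot be judged. An allergy question there would lower the practical risk but would leave the eligibility list unchanged.
- *That harm is likely, or that the comparison is biased or loses power.* With no prevalence figure, none of these can be shown.

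**Conclusion.** The omission is real. Under the stated eligibility rule, a woman with known Betadine hypersensitivity may be randomised, with a 1 in 2 chance of allocation to Betadine if she is enrolled. It is a minor safety improvement to the protocol text and should not be ranked with points that bear on the trial's conclusions. Confidence is high that the criterion is absent. It is lower for the practical consequence, which depends on how well the informal checks work and on consent pages that were not available. The conclusion rests on the eligibility list being complete as shown.

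**What to change.** Add *known allergy or hypersensitivity to Betadine/povidone-iodine* to the exclusions in section IV.b. Ask about it at Visit 1, confirm it before randomisation, and apply it to every candidate whichever arm she might be given, so that the exclusion falls equally on both arms.

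The cost is one line of protocol text and one screening question. A few women would be excluded, in a number that the documents do not allow to be estimated, at roughly 0.2 to 0.3 week of accrual each. The sample size stays as it is.
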